# 9.1 Procedures per visit

The follow-up of the patients in the present study consists of 9 scheduled visits in each period (18 in total). Depending on which arm the patient falls on, the trial treatment will begin in one period or another. That is, if after the randomization of the patient, he falls into the Experimental Arm, the treatment will begin on Visit 2 (Day 1) and will end in week 24, corresponding to period 2 as the TAU treatment period. If, on the other hand, the patient falls into Control Arm, the study will begin with a first TAU period (continues with the treatment according to clinical criteria) and it will be in period 2 when the trial treatment begins (in week 26 of the study).

In this protocol the visits are arranged in chronological order, specifying the week to which each one corresponds.

The following sections detail the procedures that must be carried out at each visit.

## 9.1.1 Visit 1: Screening (-30 days)

During the screening or selection visit (visit 1), certain actions must be carried out as a step prior to inclusion, as well as data collection prior to inclusion. The procedures that will be carried out during this visit are detailed below:

- Signature of the informed consent
- Capacity Assessment (ACE)
- Assessment of the inclusion / exclusion criteria
- In the case of women of childbearing age, a urine or blood pregnancy test will be requested (the most feasible)
- Demographic data: age, sex, race, educational level, marital status, illiteracy
- Clinical history / anamnesis with collection of: developmental data, onset of behavioural or psychotic disorders, previous treatments, family history of schizophrenia, history of epilepsy, history of prison and history of consumption habits (alcohol, tobacco and drugs)
- Diagnosis of schizophrenia
- HAMD-17
- BARS, PANSS, SAS.
- Review of concomitant medication

# 9.1.2 Visit 2: Randomization (Treatment Day 1 / Baseline Visit)

- Review of inclusion and exclusion criteria
- Physical examination: weight, blood pressure, heart rate, respiratory rate, temperature and abdominal perimeter
- Blood extraction (hemogram and biochemistry)
- Clinical, cognitive and functional evaluation: SAS, SANS, BACS, BACS App, NSA-4 and GAF
- Review of concomitant medication
- Medication administration (day 1 of treatment)

# 9.1.3 Visit 3 (Week 1: day 8 ± 3 days)

- Clinical, cognitive and functional evaluation: SAS
- Dosing and dispensing treatment
- Adherence to treatment
- Review of concomitant medication
- Review of adverse events

# 9.1.4 Visit 4 (Week 4: day 29 ± 3 days)

- Physical examination: weight, blood pressure, heart rate, respiratory rate, temperature and abdominal perimeter
- Clinical, cognitive and functional assessment: SAS, SANS and NSA-4
- Dosage and dispensing treatment
- Adherence to treatment
- Concomitant medication review
- Review of adverse events

# 9.1.5 Visit 5 (Week 8: day 57 ± 3 days)

- Clinical, cognitive and functional evaluation: SAS
- Dosing and dispensing treatment
- Adherence to treatment
- Review of concomitant medication
- Review of adverse events

# 9.1.6 Visit 6 (Week 12: 85 ± 3 days)

- Physical examination: weight, blood pressure, heart rate, respiratory rate, temperature and abdominal perimeter
- Clinical, cognitive and functional evaluation: SAS, SANS, BACS, GAF and NSA-4
- Dosing and dispensing treatment
- Adherence to treatment
- Review of concomitant medication
- Review of adverse events

# 9.1.7 Visit 7 (Week 16: day 113 ± 3 days)

- Clinical, cognitive and functional evaluation: SAS
- Dosing and dispensing treatment
- Adherence to treatment
- Review of concomitant medication
- Review of adverse events

## 9.1.8 Visit 8 (Week 20: day 141 ± 3 days)

- Clinical, cognitive and functional evaluation: SAS
- Dosing and dispensing treatment
- Adherence to treatment
- Review of concomitant medication
- Review of adverse events

# 9.1.9 Visit 9: End of Treatment Visit (Week 24: day 169 ± 3 days)

- Physical examination: weight, blood pressure, heart rate, respiratory rate, temperature and abdominal perimeter
- Clinical, cognitive and functional evaluation: SAS, SANS, BACS, PANSS, GAF and NSA-4
- Dosing and dispensing treatment
- Adherence to treatment
- Review of concomitant medication
- Review of adverse events

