#### 6.5 Follow-up

The follow-up of the patients will be carried out in the visits defined in this protocol. After signing the informed consent, patients will undergo a screening visit to confirm their eligibility for the study. If all the inclusion and exclusion criteria are correct, patients will undergo an initial evaluation and then will be randomized 1: 1 to 24 weeks of adjuvant treatment with vortioxetine or TAU.

Thereafter, patients will be seen in week 1, 4 and monthly for the next 5 months. At the end of this period, having reached week 24, the patient will undergo a washout

period of two weeks (regardless of the assigned arm) to ensure that in the case of starting the trial in the experimental arm, there will be no effect. carry-over caused by vortioxetine at the start of the second period (week 26)

There are 2 wash weeks that will take place between the two test periods (week 24 to week 26), and a second wash that will take place at the end of the second period (week 50 to week 52) (figure 1).

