# 8.1 Treatment duration and adjustments

- The duration of treatment in each arm will be 24 weeks
- To avoid carry-over effects of the medication, a 2-week washout phase will be needed from week 24 to week 26, and another 2-week washout phase at the end of the study (week 50 to 52)
- The trial will last 52 weeks in total

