#### CAVES PROTOCOL CONFIDENTIAL VERSION 1.0

Hematology/Chemistry 		Х							Х
Dispense Treatment 11		Х	Х	Х	Х	Х	Х	Х	
Compliance 12			Х	Х	Х	Х	Х	Х	Х
Concomitant Medication	X	Х	Х	Х	Х	Х	Х	Х	Х
Adverse Events			Х	Х	Х	Х	Х	Х	Х

- 1. Between week 24 and week 26 the first wash period takes place. The washing time between one period and another will be 2 weeks
- 2. HAMD-17: Hamilton Rating Scale for Depression
- 3. BARS: Behaviorally Anchored Rating Scale
- 4. PANSS: Positive and Negative Syndrome Scale
- 5. SAS: Sedation-Agitation Scale
- 6. SANS: Scale for Assessment of Negative Symptoms
- 7. BACS: Brief Assessment of Cognition in Schizophrenia
- 8. BACS App: Brief Assessment of Cognition in Schizophrenia App. Versión de la Escala BACS en aplicación para Tablets: facilitará la realización de pruebas repetidas y reducirá efectos de la práctica. Existen diferentes versiones de la prueba.
- 9. NSA-4: Negative Symptom Assessment (4-Item)
- 10. GAF: Global Functionality Assessment Scale
- 11. Vortioxetine dosage according to Summary of Product Characteristics (section 6.5 of protocol)
- 12. Patient must bring test medication at each visit for counting. Empty boxes will stay in the center
- 13. Complete blood count including leukocyte, neutrophil, hemoglobin, and platelet counts. Blood chemistry that includes the determination of sodium, potassium, creatinine, urea, lipid profile, glycemia.

CAVES PROTOCOL CONFIDENTIAL VERSION 1.0

Procedures PERIOD 2	Visit10 (Day 183±3) Week 26	Visit11 (Day 190±3) Week 27	Visit12 (Day 211±3) Week 30	Visit13 (Day 239±3) Week 34	Visit14 (Day 267±3) Week 38	Visit15 (Day 295±3) Week 42	Visit16 (Day 323±3) Week 46	Visit17 (Day 351±3) Week 50 	Visit18 (Day 379±3) Week 52
Pregnancy Test	Х								X
Medical History	Х	Х	Х	X	Х	Х	Х	Х	X
HAMD-17	Х								
BARS	Х								
PANSS	Х							Х	Х
SAS	Х	Х	X	X	Х	Х	Х	Х	
SANS	X		X		Х			Х	
BACS	X				Х			X	Х
BACS App	X							X	
NSA-4	X		X		Х			X	
GAF	X				Х			X	Х
Vitals Signs: weigth, Height, Blood Pressure, Pulse Rate, abdominal perimeter	х		х		Х			х	Х
Hematology/Chemistry	X							X	Х
Dispense Treatment	X	Х	X	Х	Х	X	X		
Compliance		Х	X	Х	Х	Х	X	X	
Concomitant Medication	X	Х	X	Х	Х	X	X	X	Х
Adverse Events	X	X	X	X	Х	X	X	X	X

1. Between week 50 and week 52 the second wash period takes place. The visit corresponding to week 52 corresponds to the FINAL VISIT OF THE TRIAL.

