# 9.1.17 Visit 17: End of Treatment Visit (Week 50: day 351 ± 3 days)

- Physical examination: weight, blood pressure, heart rate, respiratory rate, temperature and abdominal girth
- Blood extraction (hemogram and biochemistry)
- Clinical, cognitive and functional evaluation: SAS, SANS, PANSS, BACS, BACS App, NSA-4 and GAF
- Adherence to treatment
- Review of concomitant medication
- Review of adverse events
- Beginning of the washing period (two weeks)

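### The Visit 9 list (week 24) has study treatment dispensed as the washout starts, which contradicts the schedule table and the washout sections; if followed, it could put the period 2 baseline on drug

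*Protocol*

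**What the plan says.** The protocol heads section 9.1.9 "Visit 9: End of Treatment Visit (Week 24: day 169 ± 3 days", and its procedure list includes "Dosing and dispensing treatment". Section 9.1 introduces these lists as the procedures required at each visit, so the item is an operative instruction to the site.

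Other parts of the protocol treat week 24 differently:

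- In the Period 1 schedule table (section 9), the row "Dispense Treatment 11" (11 is a footnote mark) has seven marks, at Visits 2 to 8. The Visit 9 cell is empty.
- Footnote 1 to that table, attached to week 24, reads "Between week 24 and week 26 the first wash period takes place".
- Section 9.1 says that for patients who start in the experimental arm "the treatment will begin on Visit 2 (Day 1) and will end in week 24".
- Section 8.1 says "a 2-week washout phase will be needed from week 24 to week 26", and sections 2.9 and 2.17 give the same interval.
- Section 6.5 describes this as a "period of two weeks (regardless of the assigned arm"), with the stated aim that no vortioxetine effect carries over into week 26.
- Section 9.1.17, the end-of-treatment visit of period 2, has no dispensing item and ends with "Beginning of the washing period (two weeks"). Section 9.1.9 has no such line.

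**The concern.** The crossover comparison relies on the fortnight between weeks 24 and 26. Section 4 requires the first treatment's effect to be gone before period 2 starts, and section 6.1.1 makes week 26 the baseline for the period 2 change in the BACS App composite.

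Staff working from the visit list are told to issue treatment at week 24; staff working from the table are not. If treatment were issued and taken up to week 26, patients who had vortioxetine first would enter their TAU period with a baseline measured on drug. Losing the drug effect by week 50 would then be scored as decline under TAU. That error favours vortioxetine and arises in one sequence only, so it would not cancel between sequences.

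**Working it through.** **1. The texts side by side**

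| Place in the protocol | Week 24 |
|---|---|
| 9.1.9, heading | end of treatment |
| 9.1.9, list | dosing and dispensing |
| Period 1 table, dispensing row | Visits 2 to 8 marked, Visit 9 empty |
| Period 1 table, footnote 1; 2.9, 2.17, 6.5, 8.1 | washout from week 24 to week 26 |
| 9.1 | vortioxetine started at Visit 2 ends at week 24 |
| 9.1.17 (parallel visit, week 50) | no dispensing; washout begins |

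The empty cell is unlikely to be an extraction fault. The compliance row beside it runs through to Visit 9, and the Period 2 table has the same shape: dispensing is marked at Visits 10 to 16 and empty at Visit 17.

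**2. Length of the interval**

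Visit 9 is day 169 and Visit 10 is day 183: 183 − 169 = 14 days, the nominal two weeks.

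**3. Drug supply (section 2.10)**

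The plan's figure reproduces: 14 tablets for the first 2 weeks, plus 22 × 7 × 2 = 308, gives 322. Adding 10% gives 354.2, rounded up to 355. This covers 24 weeks and allots nothing to weeks 24 to 26. Two boxes of 250 are supplied per patient, however: 500 − 322 = 178 tablets over, against 14 × 2 = 28 tablets for two further weeks at the 20 mg level. Supply was not planned for the washout, but it would not prevent dosing in it.

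**4. Size of the bias if the line were followed**

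Inputs:
- D is the true effect on the change score. Section 12.1 uses 0.5 with SD 1. Its sample size reproduces: (1.960 + 0.842)² × (1/0.5)² = 31.40, and 31.40/0.85 = 36.94, so 37. The present point does not depend on it.
- r is the fraction of D still present at week 26 because drug was issued at week 24, averaged over all vortioxetine-first patients. **The documents give no value, so r is an assumption.**
- Also assumed: the effect is gone by week 50, changes under TAU are otherwise zero, there is no period effect, and the sequences are of equal size (section 6.3 randomises 1:1).

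Formulas:
- Vortioxetine-first: D − (0 − rD) = D(1 + r)
- TAU-first: D
- Pooled within-patient contrast: [D(1 + r) + D]/2 = D(1 + r/2)

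| r (assumed) | Pooled estimate for D = 0.5 | Ratio to truth |
|---|---|---|
| 0 | 0.50 | 1.00 |
| 0.25 | 0.5625 | 1.125 |
| 0.5 | 0.625 | 1.25 |
| 1 | 0.75 | 1.5 |

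Because r is an average over patients, it already includes the share actually dosed. If half took drug to week 26 with the full effect and the rest took none, r = 0.5.

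**5. Which analyses are touched**

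Section 12.2 plans a comparison between arms in period 1, the same in period 2, and a within-patient comparison across periods. The period 1 comparison uses changes up to week 24 and cannot be affected. The within-patient contrast is affected as above. The period 2 comparison uses the week 26 baseline and becomes D − (−rD) = D(1 + r).

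**The case against.** The best reply is that this is a leftover line. Visits 5 to 8 carry the same item, the heading of 9.1.9 itself says that treatment ends, and the table and the washout sections all point one way. The Visit 9 list is careless in other respects too: it omits the BACS App and the blood tests that the table marks at week 24. A site would have to override most of the protocol to dose into the washout. This stands as an argument about likelihood. It does not remove an instruction from a list whose procedures section 9.1 makes obligatory.

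Detection is also better than the week 26 visit suggests. The table has no compliance mark at Visit 10 and section 9.1.10 lists no adherence item. Section 6.7 and table footnote 12, however, provide for tablet counts at each visit. Such counts would make dosing in the washout easier to notice, though they would not prevent it.

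Section 4 mentions a stepwise reduction when vortioxetine is stopped, which could be offered as the reason for dispensing at Visit 9. It is a background remark that no treatment, washout or schedule section takes up, so it does not settle the conflict.

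Finally, issuing drug at week 24 does not establish that it is being taken at week 26. A residual effect at week 26 could also arise with no dispensing at all, if two weeks were too short. That is a separate question and is not claimed here.

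**Conclusion.** The contradiction is certain: one visit list issues treatment at week 24, while the schedule table and five other sections end treatment or begin the washout there. The statistical consequence is conditional. If drug were issued and taken to week 26, the within-patient contrast would be biased towards vortioxetine by a factor of 1 + r/2. The upper limit of 1.5 is an assumed worst case: every vortioxetine-first patient dosed, the full effect kept at week 26, and all of it lost by week 50.

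A reader might infer that the trial will overstate the effect by half, or that the protocol means patients to be dosed through the washout. The documents support neither. They give no retained fraction, no expected share of patients dosed and no sign that the line overrides the washout sections, and the period 1 comparison is untouched in any case. The point is worth correcting because week 26 is a primary-endpoint baseline and the correction is cheap, not because a bias has been shown.

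**What to change.** Reconcile section 9.1.9 with the Period 1 schedule table and its footnote 1, and with sections 2.9, 2.17, 6.5, 8.1 and 9.1, so that one consistent statement remains on dispensing at week 24 and on the washout. Which clinical rule is right is for the sponsor and the investigators and is not proposed here. The BACS App and blood-test omissions in the Visit 9 list can be checked against the table at the same time.

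If only the visit list has to change, the cost is one line. The sample size does not depend on this point.

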# 9.1.10 Visit 10 (Week 26: day 183 ± 3 days)

- In the case of women of childbearing age, a urine or blood pregnancy test will be requested (the most feasible)
- Physical examination: weight, blood pressure, heart rate, respiratory rate, temperature and abdominal perimeter
- Blood extraction (hemogram and biochemistry)
- HAMD-17
- Clinical, cognitive and functional evaluation: BARS, PANSS, SAS, SANS, BACS, BACS App, NSA-4 and GAF
- Medication administration (day 1 of treatment)
- Review of concomitant medication
- Review of adverse events

#### 9.1.11 Visit 11 (Week 27: day 190 ± 3 days)

- Clinical, cognitive and functional evaluation: SAS
- Dosing and dispensing treatment
- Adherence to treatment
- Review of concomitant medication
- Review of adverse events

# 9.1.12 Visit 12 (Week 30: day 211 ± 3 days)

- Physical examination: weight, blood pressure, heart rate, respiratory rate, temperature and abdominal perimeter
- Clinical, cognitive and functional assessment: SAS, SANS and NSA-4
- Dosage and dispensing treatment
- Adherence to treatment
- Concomitant medication review
- Review of adverse events

#### 9.1.13 Visit 13 (Week 34: day 239 ± 3 days)

- Clinical, cognitive and functional evaluation: SAS
- Dosing and dispensing treatment
- Adherence to treatment
- Review of concomitant medication
- Review of adverse events

#### 9.1.14 Visit 14 (Week 38: day 267 ± 3 days)

- Physical examination: weight, blood pressure, heart rate, respiratory rate, temperature and abdominal perimeter
- Clinical, cognitive and functional evaluation: SAS, SANS, BACS, GAF and NSA-4
- Dosing and dispensing treatment
- Adherence to treatment
- Review of concomitant medication
- Review of adverse events

# 9.1.15 Visit 15 (Week 42: day 295 ± 3 days)

- Clinical, cognitive and functional evaluation: SAS
- Dosing and dispensing treatment
- Adherence to treatment
- Review of concomitant medication
- Review of adverse events

# 9.1.16 Visit 16 (Week 46: day 323 ± 3 days)

- Clinical, cognitive and functional evaluation: SAS
- Dosing and dispensing treatment
- Adherence to treatment
- Review of concomitant medication
- Review of adverse events

# 9.1.17 Visit 17: End of Treatment Visit (Week 50: day 351 ± 3 days)

- Physical examination: weight, blood pressure, heart rate, respiratory rate, temperature and abdominal girth
- Blood extraction (hemogram and biochemistry)
- Clinical, cognitive and functional evaluation: SAS, SANS, PANSS, BACS, BACS App, NSA-4 and GAF
- Adherence to treatment
- Review of concomitant medication
- Review of adverse events
- Beginning of the washing period (two weeks)

# 9.1.18 Visit 18: End of Study Visit (Week 52: day 379 ± 3 days)

- In the case of women of childbearing age, a urine or blood pregnancy test will be requested (the most feasible)
- Physical examination: weight, blood pressure, heart rate, respiratory rate, temperature and abdominal girth
- Blood extraction (hemogram and biochemistry)
- Clinical, cognitive and functional evaluation: BACS, PANSS and GAF
- Review of concomitant medication
- Review of adverse events

#### 9.1.19 Unscheduled Visit

If a patient presents changes in their marked clinical status or there is a suspicion of an adverse event, an assessment (less than 24 hours) should be made of the need for an unscheduled visit.

To do this, the patient must have a telephone number to contact the research team in case of need due to recurrence of symptoms and an adverse event.

In the unscheduled visit the following procedures will be carried out:

- In the case of women of childbearing age, a urine or blood pregnancy test will be requested (the most feasible)
- Physical examination: weight, blood pressure, heart rate, respiratory rate, temperature and abdominal girth
- Blood extraction (hemogram and biochemistry)
- HAMD-17

- Clinical, cognitive and functional assessment: BARS, PANSS, SAS, SANS, BACS, BACS App, NSA-4 and GAF
- Adherence to treatment
- Concomitant medication review
- Review of adverse events

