# 5.2 Objectives

- **5.2.1 Principal objective:** To investigate the effect of vortioxetine on cognitive functioning and the severity of negative symptoms in the early stages of schizophrenia, measuring the change in the BACS App Scale at the beginning and end of each period.
- **5.2.2 Secondary objective:** To assess the efficacy of vortioxetine versus TAU in treating negative symptoms in newly diagnosed schizophrenia, as measured by change in severity of negative symptoms (SANS total scores, NSA-4) from baseline to completion of the study.
  - Additionally, the following secondary objectives will be evaluated. To assess the efficacy of vortioxetine versus TAU in the treatment of cognitive deficits in recently diagnosed schizophrenia, as measured by change in general functioning (GAF total score)
  - To assess the safety of vortioxetine in recently diagnosed schizophrenia patients as measured by the reporting of any serious adverse event evaluated in relation to the Experimental Treatment during the 52 weeks of the trial.
  - Evaluate the efficacy and reliability of the BACS App Vs BACS, measured by performing both scales and comparing results. The purpose is to confirm the reliability of the results when performing the BACS App as a faster and more practical model at the beginning and end of each period (Measurement time: baseline visit, week 24, week 26 and week 50) compared to the results obtained with the BACS scale performed at each trial visit (Measurement time: from consent signature to week 52).

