# 6.6 Discontinuation of study treatment and withdrawal of subjects from the study

Premature discontinuation of the clinical trial may occur due to a decision of the regulatory authorities, due to a change in the opinion of the Clinical Research Ethics Committees, due to safety and / or drug problems or indications of ineffectiveness.

It will be considered that there is a voluntary abandonment of the trial due to the refusal of the patient or legal guardian of the same to continue with the treatment or in the study, and the subject will be considered as abandonment immediately after communicating his decision to the Investigator. A patient may discontinue the trial at any time if the person, the legal representative, the investigator or the motorization committee determine that it is not in the best interest of the patient to maintain their participation.

Other reasons for discontinuation include:

- Patients with low compliance with the study drug, below 80%
- Patients requiring hospitalization for worsening psychotic disorder and / or behavioural disturbances associated with psychotic disorder.
- Patients in whom, during the study period, there is a high risk of detected suicide, according to the criteria established by Columbia University according to the risk assessment with the C-SSRS scale.
- Female patients who test positive for urine pregnancy at any time during their participation in the study.
- Any serious adverse event that recommends withdrawal at the discretion of the investigator with the agreement of the monitoring committee.
- The patient decides not to continue with the trial.
- Others: The researcher, as well as the sponsor, reserve the right to interrupt the study at any time for reasonable medical and / or administrative reasons.

Patients who drop out after randomization will not be replaced.

Patients who terminate treatment prematurely will complete an early termination interview and a safety visit.

The patient who has completed the protocol is considered to be one who has completed all the visits included in the 52-week follow-up period.

The interruption of the treatment does not imply that the case is excluded from the statistical analysis. These subjects will be part of the study and will be taken into account when analyzing the data.

There may be other circumstances for the abandonment, which in its case the researcher must make sure that the patient has abandoned the study, and will verify the causes of said abandonment.

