#### The domains evaluated are:

- Verbal memory, evaluated through the word list test.
- Working memory, evaluated through the digit sequence test.
- Motor speed, assessed through the token motor test.
- Verbal fluency, assessed through the word generation test.
- Attention, evaluated through the symbol code test.
- Executive functions, assessment through the Tower of London test.

Two versions of the instrument were created in order to repeat the test avoiding the recall effect.

For correction, an overall score and scores are obtained for each of the tests included. The possible scores for each of the tests are:

- Word list test: 0-75 points.
- Digit sequence test: correct answers 0-28 points; longest sequence remembered 0-8 points.
- Token motor test\_ 0-100 points.

Symbol code test: 0-110 points.

Tower of London: 0-22 points

Administration time: 30-60 minutes.

Psychometric properties of the BACS scale:

The results showed that all tests are capable of discriminating between patients with schizophrenia and healthy subjects. In the Spanish version, the concurrent validity was similar to that reported in other languages.

Other variables of clinical improvement in terms of severity of negative symptoms are measured with the total score of SANS and NSA-4 and improvement in general functioning evaluated with changes in GAF.

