#### 12.- STATISTICS

# 12.1 Sample size calculation

As it is a crossover design, each individual acts as their own control, that is, an initial treatment is assigned and after a while it is changed. Therefore, the correct thing to do would be to calculate the sample under the premise of related or paired samples, for this case it would be the dependent samples T test.

The sample size can be calculated in two ways, in the first one, the difference in the means to be detected of the primary variable (BACS), the standard deviations of the treatment change, and the correlation coefficient must be established; while the second is to consider the difference in the means to be detected for the primary variable (BACS) and the standard difference of the differences.

Accepting an alpha risk of 0.05 and a beta risk of 0.2 in a bilateral contrast, 37 subjects are required to detect a difference equal to or greater than 0.5 units. A standard deviation of 1 is assumed. A loss to follow-up rate of 15% has been estimated.

That is, based on the previous parameters, and using a confidence level of 95% and power of 80%, 37 subjects are needed.

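### The BACS App is obligatory at every unscheduled visit, where the primary endpoint does not use it, but is not listed at early termination, where the analysis could

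*Protocol*

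**What the plan says.** Section 6.1.1 defines the primary endpoint as change in the BACS App composite Z score within each period, measured at baseline, week 24, week 26 and week 50. The schedule tables in section 9 place the App at those four visits only. The secondary objectives give the same intent: "performing the BACS App as a faster and more practical model at the beginning and end of each period".

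Section 9.1.19 covers unscheduled visits. The trigger is "changes in their marked clinical status or there is a suspicion of an adverse event", after an assessment of whether a visit is needed. The procedures listed for such a visit are obligatory and include "Clinical, cognitive and functional assessment: BARS, PANSS, SAS, SANS, BACS, BACS App, NSA-4 and GAF". There is no exception for cognitive tests and no rule on which test version to use.

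The protocol treats practice as a threat. Of the BACS it says "Two versions of the instrument were created in order to repeat the test avoiding the recall effect". Note 8 to the Period 1 schedule, repeated in Annex V, says that the App comes in different versions and will reduce practice effects. It does not say how many versions there are.

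For patients who stop early, 6.6 says "Patients who terminate treatment prematurely will complete an early termination interview and a safety visit". It names no scale. Neither the schedule tables nor 9.1.1 to 9.1.19 describe this visit, and 7.3.4 refers withdrawn patients to usual care. Section 6.6 nevertheless keeps patients who interrupt treatment in the analysis.

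**The concern.** The primary test is required at visits where the primary endpoint does not use it, and is not listed at a visit where the analysis could use it.

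**Unscheduled visits.** An extra test before week 24 or 50 adds practice to the end-of-period score. Because the visits are triggered by events, the number of exposures is itself an outcome and can differ between the vortioxetine and TAU periods. A period effect in the model would not absorb such a difference, because it follows treatment and not period. The BACS alone takes 30 to 60 minutes according to 10.1, in a patient who is being seen for deterioration or a suspected adverse event.

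**Early termination.** A patient who stops before week 24 or week 50 has no prescribed end-of-period measurement of the primary endpoint. The ITT population in 12.3 is all randomized patients. The clinically evaluable population admits patients who interrupted treatment because of an adverse effect, provided that at least one variable was measured at the end of treatment or last follow-up. No listed procedure ensures that this variable is the App.

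**Working it through.** **1. The planning figure.** Section 12.1 states: "Accepting an alpha risk of 0.05 and a beta risk of 0.2 in a bilateral contrast, 37 subjects are required". The target difference given there is 0.5. On the spread the section says: "A standard deviation of 1 is assumed". The stated loss to follow-up is 15%. Reading the SD as that of the paired difference, with a normal approximation:

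n = ((1.960 + 0.842) × 1 / 0.5)² = 31.40; 31.40 / (1 − 0.15) = 36.94, so 37.

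The stated 37 is reproduced. The yardsticks used below are therefore a target of 0.5, an SD of 1 and 37 × 0.85 = 31.45 expected completers.

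**2. Exposure to the two tests before each primary assessment, from the schedule tables.**

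- Before week 24: App and BACS at baseline, BACS at week 12. That is 3 administrations; one unscheduled visit makes it 5.
- Before week 50: App at baseline and weeks 24 and 26 (3), BACS at baseline and weeks 12, 24, 26 and 38 (5). That is 8; one unscheduled visit in period 2 makes it 10.

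An unscheduled visit is thus a real addition, but to patients who have already been tested repeatedly.

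**3. Size of a possible practice bias.** The documents give no input, so every figure in the first two columns below is an assumption. Let d be the excess share of patients with an extra test under one treatment and g the gain in z per extra test that persists to the end of the period. Then

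bias = d × g.

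With s = bias × √31.45, the two-sided type I error is 1 − Φ(1.96 − s) + Φ(−1.96 − s).

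| d | g (z) | bias (z) | share of 0.5 | type I error |
|---|---|---|---|---|
| 0.10 | 0.05 | 0.005 | 1% | 0.050 |
| 0.20 | 0.10 | 0.02 | 4% | 0.051 |
| 0.20 | 0.20 | 0.04 | 8% | 0.056 |
| 0.30 | 0.30 | 0.09 | 18% | 0.080 |
| 0.50 | 0.30 | 0.15 | 30% | 0.134 |

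The last row needs the extreme of both ranges. If the excess lies in the TAU periods, the bias has the same size with the opposite sign.

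**4. Patients without a prescribed end-of-period score.** 0.15 × 37 = 5.55, so about 5 to 6 patients at the protocol's own loss rate. This is a planning figure. Some of these patients may attend no visit at all, so the number whose score could be recovered is not known.

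**5. Does the choice of primary measure matter?** Section 10.1 names the BACS total score throughout the trial, while 6.1.1 names the App at four time points. Both tests are on the 9.1.19 list, so the exposure point is the same on either reading. The wording of 10.1 also means that off-schedule scores are not excluded everywhere in the protocol.

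**The case against.** A reader might infer that unscheduled visits are mostly treatment-related, so that practice gain is credited to vortioxetine. The documents do not support this. The trigger covers any marked clinical change or suspected adverse event in either period, a visit follows only an assessment of need, and 9.1.19 also names recurrence of symptoms as a reason for contact, which could bring in TAU patients as readily. Some of the most serious cases would be withdrawn under 6.6 and 7.3, so an extra test could not inflate a week 24 or 50 score that is never taken. More visits on vortioxetine is plausible but is not stated.

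A reader might also infer that an unscheduled test uses up a version needed later. The statement about two versions concerns the BACS; the number of App versions is not given, so this is not shown.

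A third inference is that early terminators are denied the App. The protocol leaves the content of that visit undefined and does not exclude the App. A patient who stops because of an adverse event might receive it through an unscheduled visit.

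Two further objections have some force. Section 6.1.1 already confines the primary endpoint to four time points, so off-schedule scores are outside that definition, and the handling of missing data belongs in a SAP. Second, the reliability objective in 5.2.2 refers to the BACS at each trial visit, so removing it from 9.1.19 moves away from that wording.

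What stands after this is narrower: which assessments are made at which visit is for the protocol to fix, and no SAP can recover an App score that was never collected.

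**Conclusion.** The point holds as a cheap improvement to visit procedures. Section 9.1.19 makes both cognitive tests obligatory at event-triggered visits that the endpoint in 6.1.1 does not use, so test exposure before the primary assessments can differ by treatment. The direction is unknown. The size cannot be computed from the documents and is probably small, because alternate versions reduce practice effects: 0.02 to 0.04 z under moderate assumptions, 0.005 to 0.15 z over the full assumed range. This does not show that the trial's comparison is biased in favour of vortioxetine.

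The early-termination gap is the firmer half. Patients who stop treatment remain in the analysis, yet no App assessment is listed for them. At the stated 15% loss that is about 5 to 6 of 37, on the assumption that those lost are patients who stop before an end-of-period visit.

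**What to change.** - In 9.1.19, remove the BACS App from the list. Remove the BACS as well, unless the reliability objective is meant to use it at unscheduled visits. Keep the other items.
- In 6.6, list the BACS App among the assessments of the early-termination visit, and add that visit to section 9.
- State that App scores from unscheduled visits do not enter the primary analysis, and that early-termination scores are flagged by time of assessment. How the flagged scores are then used can be left to the SAP.

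The cost is a few lines of text and one short App test at a visit that already exists. Unscheduled visits become shorter. What is lost is a cognitive score at the time of an event and a few paired BACS and App results for the reliability objective.
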